	
treatment criteria"). After the first treatment cycle is completed, all subjects may enter the open label extension phase and will be dosed with BoNT/A-DP (20 U) for subsequent re-treatments.
 
Evaluation for re-treatment takes place at the earliest at 12 weeks after the first/previous treatment. Subjects who do not qualify for re-treatment at week 12 will have the option (pending eligibility) of re-treatment at a later visit (at 4weekly intervals thereafter) until they are eligible for re-treatment or until a total of 48 weeks has elapsed since study start. Subjects will attend for visits at 1 and 4 weeks after any re-treatment and at 4 weekly intervals thereafter. At week 2 and week 8 of each open label cycle a telephone call visit will take place. According to the study schedule (Section 2.1 and Section 0), a maximum of 4 treatments per subject (4 treatment cycles) is permitted during the study time frame, with treatments separated by a minimum of 12 weeks.
 
The number of treatments administered per subject will depend on the subject's qualification for re-treatment; however, the last opportunity for re-treatment is at week 48.

Planned Duration of Subject Participation
	
Participation is anticipated to last up to 62 weeks.

Primary Outcome Measure
	
The primary endpoint is the proportion of subjects among BoNT/A-DP and placebo groups with a Facial Wrinkle Scale (FWS) score of 0 or 1 and an improvement of ≥ 2 points in FWS score (at maximum frown) at week 4 visit (of the first treatment cycle) relative to baseline(responders), based on both the investigators'and the subjects'in-clinic assessments. Thus, the primary endpoint is a composite endpoint comprising investigator and subject assessments of treatment effectiveness.

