6.3.1 First Treatment Cycle

The first treatment cycle of the study will comprise two treatment groups as follows:

- Group A (active): BoNT/A-DP (20 units, 0.5 mL).
- Group B (placebo control): sterile, 0.9% sodium chloride (0.5 mL).

Eligible subjects will be randomized at baseline (day 0) to Group A or B to receive the first treatment in a 3:1 randomization scheme, respectively. Investigators and subjects will be blinded to the treatment administered and will evaluate the severity of glabellar lines independently. The subjects must perform their assessment independently and ideally before the investigator, to ensure they are not biased by the investigator. The same investigator must assess the subject at baseline and at the visits at weeks 1, 2 and 4 in the first treatment cycle.

After a screening period of up to 14 calendar days, subjects will receive the first treatment (BoNT/A-DP or placebo) and attend for visits at 1, 2 and 4 weeks after treatment and at 4-weekly intervals thereafter for evaluation of efficacy and safety (primary and key secondary efficacy endpoints will only be evaluated in the first treatment cycle in comparison with placebo). Re-screening will not be permitted.

The effect of botulinum toxin typically lasts a few months, hence the first treatment cycle will last at least 12 weeks and will end when the subjects qualify for re-treatment (in accordance with the "eligibility for re-treatment criteria" as outlined in Section 7.3). Efficacy duration of four to six months³⁶ or 17.1 ± 6.5 weeks³⁵ have been reported from other studies, hence the study is designed flexibly to adequately assess the duration of effect compared with placebo in the first treatment cycle.

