7.3 Eligibility Criteria for Re-treatment

The following criteria **MUST** be met for re-treatment:

- At time of re-treatment subject does not have relevant changes to their health status from enrollment, which would have prevented subject's entry into the study according to the inclusion and exclusion criteria.
- The subject must have been randomized to receive treatment and must have received at least one treatment (BoNT/A-DP or placebo).
- A minimum of 12 weeks must have elapsed since the previous study treatment.
- The subject's glabellar lines at maximum frown must have relapsed to a FWS score of 2 or 3 as determined by both the investigator and the subject.
- No relevant infection or inflammation in the planned injection area.
- Negative urine pregnancy test, in women of child-bearing potential.
- The subject must have received fewer than four study treatments.
- The subject must agree and consent to re-treatment.
- Re-treatment will be performed at the latest by week 48.

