Adverse events will be separated to pre-treatment AEs and TEAEs. TEAEs are defined as all AEs with onset or worsening (increase in severity) after receiving first dose of study medication (independent of whether it is BoNT/A-DP or placebo). If it cannot be determined whether an AE is treatment-emergent due to a partial onset date, then it will be counted as such.

TEAEs will be analyzed overall (for BoNT/A-DP or placebo), and for BoNT/A-DP treatment group additionally separately per first treatment cycle or open label extension phase: events starting on or after first treatment up to before open label extension (first cycle), and events starting on or after re-treatment until end of study (open label phase). If it cannot be determined whether an AE started during the first treatment cycle or the open label extension phase due to a partial onset date, then it will be counted as having started during first treatment cycle.

Events of subjects who started the first treatment with placebo but then entered the open label extension for re-treatment with BoNT/A-DP will be considered to placebo for the first cycle and to BoNT/A-DP for the open label phase.

Treatment-emergent adverse events will be summarized by system organ class (SOC) and preferred term (PT) (MedDRA). The number of events, as well as the number and rate of affected subjects will be reported. TEAEs (SOC and PT) will also be summarized by seriousness, severity, relationship to study medication, and relationship to procedure. Treatment-emergent AESIs will be tabulated separately.

Analysis of secondary safety endpoint 2 (antibody formation):

The presence of antibodies will be summarized by counts and percentages of subjects by treatment group and time point. For the subgroup of subjects with a sample test positive for anti-drug antibodies, all analyzed samples will be analyzed descriptively by counts over time as well.

Analysis of secondary safety endpoint 3 (laboratory data, vital signs, ECG):

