3.3 Study treatments and assessments

Subjects will participate in this study for a duration of 50 to 62 weeks from signing the informed consent form (ICF) to the End of Study visit (i.e. up to 14 calendar days for screening, followed by 48 to 60 weeks study participation).

The first treatment cycle of the study will comprise two treatment groups as follows:

- Group A (active): BoNT/A-DP (20 units, 0.5 mL).
- Group B (placebo control): sterile, 0.9% sodium chloride (0.5 mL).

Eligible subjects will be randomized at baseline (day 0) to Group A or B to receive the first treatment in a 3:1 randomization scheme, respectively. Investigators and subjects will be blinded to the treatment administered and will evaluate the severity of glabellar lines independently. The subjects must perform their assessment independently and ideally before the investigator, to ensure they are not biased by the investigator. The same investigator must assess the subject at baseline and at the visits at weeks 1, 2 and 4 in the first treatment cycle.

After a screening period of up to 14 calendar days, subjects will receive the first treatment (BoNT/A-DP or placebo) and attend for visits at 1, 2 and 4 weeks after treatment and at 4-weekly intervals thereafter for evaluation of efficacy and safety (primary and key secondary efficacy endpoints will only be evaluated in the first treatment cycle in comparison with placebo). Re-screening will not be permitted.

Statistical Analysis Plan (SAP)

The effect of botulinum toxin typically lasts a few months, hence the first treatment cycle will last at least 12 weeks and will end when the subjects qualify for re-treatment.

After the first treatment cycle is completed, all subjects may enter the open label extension phase and will be dosed with BoNT/A-DP (20 U) for subsequent re-treatments.

Subjects will attend for visits at one and four weeks after re-treatment and at 4-weekly intervals thereafter. Additional telephone call follow-ups will take place in the open label extension phase two and eight weeks after each re-treatment. Each re-treatment cycle will last at least 12 weeks and will end when the subject qualifies for re-treatment or with the End of Study visit. According to the study schedule, a maximum of four treatments per subject (four treatment cycles) is permitted during the study time frame, with treatments separated by a minimum of 12 weeks.

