8.5 Extent of exposure

8.5.1 Duration of study drug exposure

Duration of study drug exposure (in days) will be calculated as date of last study medication administration minus date of first study medication administration + 1 day, regardless of study drug interruption.

Study drug exposure will be summarised by treatment group and separated for the double-blind and open label phase on the Safety Analysis Set using time intervals and summary statistics. Planned and actual dose as well as injections at all sites per subject and treatment cycle will be listed.

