8.7.2 Adverse events (secondary safety endpoint 1)

All AEs will be classified by SOC and PT according to MedDRA Version 19.0 or higher.

In summaries by SOC and PT, adverse events will be sorted by decreasing frequency within each SOC and PT. In summaries by PT, AEs will be sorted by decreasing frequency within each PT.

AE summary tables will be presented for TEAEs and AESIs separately by treatment cycle and will include the number and percentage of subjects with any:

- TEAE/AESI
- TEAE/AESI related to study medication (AE will be defined as related if causality is definitely, probably or possibly or if causality assessment is missing)
- TEAE/AESI related to injection procedure (AE will be defined as related if causality is definitely, probably or possibly or if causality assessment is missing)
- Severe TEAE/AESI

Statistical Analysis Plan (SAP)

- Severe TEAE/AESI related to study medication
- Severe TEAE/AESI related to injection procedure
- TEAE/AESI leading to discontinuation
- Study drug related TEAE/AESI leading to discontinuation
- Serious TEAE/AESI
- TEAE/AESI leading to death.

All TEAEs as well as all AESIs will be summarized by SOC, PT and treatment group using frequency counts and percentages (i.e. number and percentage of subjects with an event).

The number of events, as well as the number and rate of affected subjects will be reported by SOC and PT for all TEAEs and for all AESIs separately.

Adverse events will be separated to pre-treatment AEs and TEAEs. TEAEs are defined as all AEs with onset or worsening (increase in severity) after receiving first dose of study medication (independent of whether it is BoNT/A-DP or placebo). If it cannot be determined whether an AE is treatment-emergent due to a partial onset date, then it will be counted as such.

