TEAEs and AESIs will be analyzed overall (for BoNT/A-DP or placebo), and for BoNT/A-DP treatment group additionally separately per first treatment cycle or open label extension phase: events starting on or after first treatment up to before open label extension (first cycle), and events starting on or after re-treatment until end of study (open label phase). If it cannot be determined whether an AE started during the first treatment cycle or the open label extension phase due to a partial onset date, then it will be counted as having started during first treatment cycle. The assignment of AEs to the different cycles of the open label extension phase will be done similarly: AEs will be assigned to a certain cycle if they start on or after treatment of the respective cycle but before treatment of the next cycle. In case that there is no subsequent treatment cycle, all AEs (starting on or after the last treatment) until end of study will be assigned to the last cycle.

Events of subjects who started the first treatment with placebo but then entered the open label extension for re-treatment with BoNT/A-DP will be considered to placebo for the first cycle and to BoNT/A-DP for the open label phase.

TEAEs and AESIs (per SOC and PT) will also be summarized by seriousness, severity, relationship to study medication, and relationship to procedure using frequency counts and percentages (i.e. number and percentage of subjects with an event).

Statistical Analysis Plan (SAP)

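### First-cycle adverse event percentages cover a window that ends at loss of effect, so BoNT/A-DP is expected to be observed longer than placebo and to show more late-accruing events even with no drug effect

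*SAP*

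**What the plan says.** Protocol 6.3.1 describes an efficacy-driven cycle: "hence the first treatment cycle will last at least 12 weeks and will end when the subjects qualify for re-treatment". SAP 3.3 repeats this. Under Protocol 7.3 the lines "must have relapsed to a FWS score of 2 or 3 as determined by both the investigator and the subject". Eligibility is checked at week 12 and every four weeks after that, and the Synopsis states that "the last opportunity for re-treatment is at week 48". The first cycle can therefore last from 12 to 48 weeks.

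SAP 8.7.2 defines first-cycle events as "events starting on or after first treatment up to before open label extension (first cycle"). It summarizes them as "frequency counts and percentages (i.e. number and percentage of subjects with an event"). It also mentions a rate of affected subjects but gives it no person-time denominator. Neither document plans a common-window table, an incidence per subject-time or a time-to-first-event analysis for safety.

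SAP 8.5.1 defines exposure as "date of last study medication administration minus date of first study medication administration + 1 day", and SAP 8.7.1 summarizes that variable for each cycle. Protocol 12.4.2 adds a pooled summary: "TEAEs will be analyzed overall (for BoNT/A-DP or placebo"). Only the BoNT/A-DP events are then split by phase. Events that placebo starters have after re-treatment are attributed to BoNT/A-DP.

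**The concern.** The adverse event window closes on the outcome that the drug is meant to change. A subject who still benefits stays in the first cycle and can go on reporting events; a subject without benefit leaves at week 12. Background events accumulate with time, so part of the difference between the arms in the percentage with an event measures duration of effect and not safety.

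The first cycle is the only placebo-controlled safety evidence in the trial, and Protocol 4.5.1.1 justifies the number of placebo subjects partly by safety comparisons. The planned exposure variable cannot show the imbalance. A cycle contains one injection, so last minus first administration plus one day equals 1 day for everyone, however long follow-up lasted. Cycle-to-cycle comparisons in the extension have the same weakness, because those cycles also vary in length.

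**Working it through.** **Plan's own figures.** The documents state neither an expected cycle length by arm nor an expected adverse event percentage, so there is nothing to reproduce on this point. The response assumptions used below (60% and 10%) come from the sample-size section. Its 42 + 14 = 56 is reproduced by the continuity-corrected two-proportion formula at one-sided 0.025 and 90% power.

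**Inputs.**
- Event level: 28.4% of the BoNT/A-DP arm of HG-11-01 (Protocol 4.4.2.1), with 16 weeks of follow-up (Table 4-2). This is an all-cause figure from an active arm, used here as an assumption for background.
- Duration of effect: a median of 85 days (12.1 weeks) and 17.1 ± 6.5 weeks (Protocol 4.5.1.2). No spread is given for the first, so an SD of 4 is assumed.
- Placebo: everyone leaves at week 12 (assumption).
- No drug effect on adverse events.

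**Model.** Weekly hazard h = −ln(1 − 0.284)/16 = 0.0209. The percentage with an event by week t is 1 − exp(−h·t):

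| Week | 12 | 16 | 20 | 24 | 28 | 32 | 36 | 40 |
|---|---|---|---|---|---|---|---|---|
| % with event | 22.2 | 28.4 | 34.1 | 39.4 | 44.3 | 48.7 | 52.8 | 56.6 |

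The cycle ends at the first four-weekly visit, from week 12 on, at or after loss of effect. With a normal distribution of duration, the share ending at each visit is:

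| Week | 12 | 16 | 20 | 24 | 28 | 32 | 36 | 40 |
|---|---|---|---|---|---|---|---|---|
| 17.1 ± 6.5 | 0.216 | 0.217 | 0.239 | 0.184 | 0.097 | 0.036 | 0.009 | 0.002 |
| 12.1 ± 4 | 0.490 | 0.345 | 0.141 | 0.023 | 0.001 | – | – | – |

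Multiplying each share by its percentage and summing gives:
- 17.1 weeks: mean cycle 19.5 weeks, 33.0% with an event against 22.2% on placebo, excess 10.8 points.
- 12.1 weeks: mean cycle 14.8 weeks, 26.4% against 22.2%, excess about 4.3 points before rounding.

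**Allowing for non-responders.** If 60% of the active arm follows these durations and 40% leaves at week 12, the excess is 0.6 × 10.8 = 6.5 points, or 0.6 × 4.26 = 2.6 points.

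**Sensitivity.**
- *Some placebo subjects stay.* Assume 10% are not eligible at week 12 and that this share halves every four weeks. Placebo then averages 12.8 weeks and 23.3%. With 60% responders and SD 6.5, the active arm shows 26.0%, 29.1% and 32.5% for durations centred on 12.1, 17.1 and 21.7 weeks (the last an assumed centre for the cited four to six months). The excesses are 2.7, 5.8 and 9.2 points.
- *More responders.* With 89.3%, the investigator-rated response in HG-11-01, the active figures are 27.3%, 32.0% and 37.0%, and the excesses 4.0, 8.7 and 13.7 points.
- *Lower background.* Taking the 9.0% with treatment-related events off 28.4% leaves 19.4% as a rough lower bound. In the 60% case with placebo leaving at week 12, the excess is then 1.8 points (12.1 weeks) or 4.8 points (17.1 weeks).
- *Early events.* If 75% of the 16-week hazard falls in the first four weeks, and some placebo subjects stay as above, placebo shows 26.8%. The active arm shows 27.7% (60% responders, 12.1 weeks) to 29.7% (89.3%, 17.1 weeks), an excess of about 1 to 3 points.

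**With a common window.** Counting only the first 12 weeks gives 22.2% in both arms, a difference of 0. Incidence per subject-week is also equal, at 0.0209.

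**The case against.** Safety is descriptive, with no between-arm testing. SAP 8.7.2 already separates tables by cycle and gives separate rows to drug-related, procedure-related and severe events and separate tables to AESIs. The distortion runs against the drug, so it should not hide a true excess. Onset dates would allow a windowed table later without new data. This lowers the stakes but does not remove the problem: with no testing or modelling, the side-by-side percentages are the controlled safety comparison. The separate rows are themselves percentages over the same unequal window.

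A reader might infer that BoNT/A-DP subjects leave much later and that the excess is about 11 points. The documents do not establish this. Protocol 6.1 anticipates an effect of approximately 12 weeks, and under the 12.1-week scenario about half of the subjects with an effect are re-treated at week 12. Under the 17.1-week scenario, 10.8 points needs every active subject to have that duration.

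A reader might also infer that the overall summary sets up to 60 weeks of BoNT/A-DP against one placebo cycle as a formal comparison. The text calls for an overall analysis by treatment, and the table layouts are in a separate document. No such comparison can be read from it, although the follow-up behind the two columns is plainly unequal.

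Finally, demoting the whole-cycle tables would push later controlled AESIs into second place, and deleting the overall summary would depart from Protocol 12.4.2. Both objections stand, and neither step is needed.

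**Conclusion.** The point holds as a cheap improvement. The first-cycle window is set by loss of effect, the summary is a crude percentage, and nothing planned corrects for unequal follow-up. In every scenario computed the active arm shows the higher percentage with no drug effect.

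A fair size at the planned 60% response is about 2.6 to 6.5 points for the 12.1- and 17.1-week durations. It is nearer 1 to 3 points if events cluster early, and larger if the four-to-six-month duration or a higher response applies.

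These figures rest on a hazard borrowed from an active arm, on normally distributed durations, and on placebo leaving at or near week 12, which is inferred and not stated. The 60% is itself only a proxy for who stays. A subject who improves from 2 to 1 fails the composite endpoint but is not eligible for re-treatment, so some non-responders in either arm will also remain past week 12. The direction is firmer than the size. Events confined to the first weeks after injection are little affected.

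**What to change.** In SAP 8.7.2, keep the planned whole-cycle tables and add two analyses beside them:

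1. Double-blind TEAE and AESI tables by arm for events with onset from first treatment to the earliest of week 12, re-treatment or withdrawal. State the cut-off day in advance, consistent with the ±2-day visit window. Day 82 (84 − 2), for example, is shared by everyone on schedule.
2. Incidence per subject-time by arm. Measure follow-up from injection to re-treatment or end of study, and not with the exposure variable of SAP 8.5.1.

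State that the between-arm safety comparison rests on these two. Use the same 12-week window when comparing cycles. Keep the overall summary that the protocol asks for, but show subject-time with it and do not present it as BoNT/A-DP versus placebo.

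The cost is extra adverse event tables from dates already collected, with no change to conduct. Events after week 12 would appear only in the whole-cycle and subject-time tables.

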7.2.2 Handling of missing or incomplete dates

7.2.2.1 Imputation rules for missing or partial AE start date:

If only Day of AE start date is missing:

If the AE start year and month are the same as that for the first dose date, then:

- If the full (or partial) AE end date is NOT before the first dose date or AE end date is missing, then impute the AE start day as the day of first dose date.
- Otherwise, impute the AE start day as 1.

Otherwise, if the AE start year and month are not the same as that for the first dose date, then impute the AE start day as 1.

Compare the imputed AE start date with treatment period to determine whether the AE is pre-treatment AE or treatment emergent adverse event (TEAE).

If only Day and Month of AE start date are missing:

If AE start year = first dose year, then:

- If the full (or partial) AE end date is NOT before the first dose date or AE end date is missing, then impute the AE start Month and Day as the Month and Day of first dose date;

- Otherwise, impute the AE start Month as January and the AE start Day as 1.

Otherwise, if AE start year not equal first dose year, then impute the AE start Month as January and the AE start Day as 1.

Compare the imputed AE start date with treatment period to determine whether the AE is pre-treatment AE or TEAE.

If Year of AE start date is missing:

If the year of AE start is missing or AE start date is completely missing then query site with no imputation. Also compare the full (or partial) AE end date to the first dose date. If the AE end date is before the first dose date then the AE should be considered as a pre-treatment AE. Otherwise, the AE will be considered as TEAE.

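### In placebo-first subjects, an adverse event whose partial onset date straddles the switch to BoNT/A-DP is reported under placebo

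*SAP*

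**What the plan says.** SAP 8.7.2 sets the rule for an event that a partial date cannot place in one phase or the other: "then it will be counted as having started during first treatment cycle". Protocol 12.4.2, under secondary safety endpoint 1, has the same rule. The next paragraph of SAP 8.7.2 says that events of subjects who began on placebo and then entered the extension "will be considered to placebo for the first cycle and to BoNT/A-DP for the open label phase".

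For known dates the cycle is clear: an event belongs to the cycle whose treatment it follows, from the day of that injection until the next one.

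SAP 7.2.2.1 imputes partial onset dates. With only the day missing, an event in the month of the first dose gets the first-dose date, unless it had already ended by then. In any other month the rule differs: if the known parts "are not the same as that for the first dose date, then impute the AE start day as 1". With day and month missing, the first-dose date is used in the first-dose year, with the same end-date condition; and "if AE start year not equal first dose year, then impute the AE start Month as January and the AE start Day as 1". The stated use of the imputed date is limited: "Compare the imputed AE start date with treatment period to determine whether the AE is pre-treatment AE or TEAE". Re-treatment dates are not mentioned.

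I found no exception for placebo-first subjects, no use of the event's end date to settle the cycle, and no sensitivity analysis with the reverse assignment.

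**The concern.** For a placebo-first subject the boundary between cycle 1 and the extension is also the boundary between saline and BoNT/A-DP. A default to cycle 1 is therefore a default to placebo. SAP Table 1 (footnote 2) puts the end of the cycle and the re-treatment on the same day, so no gap separates the two treatments. The events most exposed are those in the first weeks after the injection.

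Elsewhere the plan resolves doubt against the active drug. SAP 8.7.2 counts an event as treatment-emergent when a partial date leaves this open, and as related when causality is missing. SAP 7.2.2.1 moves an ambiguous onset around the first dose to the dose date. At the placebo-to-active switch the default goes the other way.

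At stake are a placebo rate that contains possible BoNT/A-DP events and an open-label BoNT/A-DP count that lacks them, in a trial with a stated objective of building a safety database for approval (SAP 2.2, objective 3).

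**Working it through.** The documents give no figure to reproduce, so the check applies the written rules to dates.

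**When the rule bites.** Let r be the date of the first BoNT/A-DP injection in a placebo-first subject and t a true onset on or after r.

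- Day missing: the phase is ambiguous if the first of the month of t is before r.
- Day and month missing: it is ambiguous if 1 January of the year of t is before r.
- The first-dose-month exception in SAP 7.2.2.1 cannot help when only the day is missing, because r is at least 12 weeks after the first dose (protocol 7.3).

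**Example.** Placebo on 20 June 2016, BoNT/A-DP on 12 September 2016 (week 12). An event on 17 September recorded as September 2016 could precede or follow the injection, so it goes to cycle 1 and to placebo. Day-1 imputation gives 1 September and the same result. An event on 4 October recorded as October 2016 can only follow the injection and goes correctly to BoNT/A-DP.

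**Share of true post-switch events credited to placebo, given a partial date.** Assumptions: 365 consecutive first-dose dates from 1 February 2016; re-treatment at week 12, 16 or 20; onset uniform over the window; end date not used.

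| Onset window after the switch | Day missing | Day and month missing |
|---|---|---|
| Day 0 | 96.7% | 99.7% |
| Days 0–6 | 86.8% | 98.9% |
| Days 0–13 | 75.3% | 97.9% |
| Days 0–27 | 52.3% | 96.0% |
| Days 0–83 | 17.5% | 88.4% |

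The first row can be checked by hand. With the day missing, a day-0 event escapes only if r is the first of a month: (365 − 12)/365 = 96.7%. With day and month missing it escapes only if r is 1 January: 364/365 = 99.7%. The shares are the same for all three re-treatment weeks, and the same whether the SAP 8.7.2 default or the imputed date decides the cycle. They are conditional on a partial date and say nothing about how often one occurs.

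**Effect of one subject.** With 175 placebo subjects planned (SAP 5), 1/175 = 0.57 percentage points, or zero if the subject is already counted in that row of the table.

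**Effect on the between-arm contrast.** The rule also pulls events back into cycle 1 in the 525 BoNT/A-DP-first subjects. Suppose, for illustration only, that 5 placebo-first subjects are newly affected and that the per-subject rate is equal in both groups:

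- Placebo cycle 1: 5/175 = +2.86 points.
- Active cycle 1: 15/525 = +2.86 points.
- Change in the difference: 0.

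If only 80% as many BoNT/A-DP-first subjects were affected because fewer were re-treated (assumed): 12/525 = +2.29 points, a net narrowing of 2.86 − 2.29 = 0.57 points.

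**The case against.** A reader might infer that the rule always shifts ambiguous events away from the active drug and so narrows the placebo-controlled safety contrast. The documents do not support that. Three quarters of subjects receive BoNT/A-DP first. For them every event stays with BoNT/A-DP, and the rule raises the active cycle 1 count. As shown above, the two shifts may largely cancel.

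Partial dates may also be rare. After each re-treatment there is a 30-minute observation, a week 1 visit, a week 2 call, a week 4 visit and a week 8 call (protocol Table 9-1). Events of special interest are actively asked about, and these and serious events must be reported within 24 hours (protocol 11.6.1). Safety is descriptive, without between-group tests (SAP 8.7), and all subject data are listed (SAP 8.1), so affected events can be inspected. All of this stands and limits the size of the problem.

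Two textual objections carry less weight. The imputation in SAP 7.2.2.1 is stated only for separating pre-treatment from treatment-emergent events; true, but the SAP 8.7.2 default produces the result alone. The default also follows directly on a sentence about splitting the BoNT/A-DP group by phase, so it might be read as confined to that group. Its wording has no such limit, and on that reading ambiguous events in placebo-first subjects would have no rule at all.

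None of this removes the misattribution in placebo-first subjects.

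**Conclusion.** The point holds for placebo-first subjects. It concerns events whose known date parts cover time both before and after the first BoNT/A-DP injection; partial dates in a later month are placed correctly. For the straddling events the treatment label itself may be wrong, in the direction that favours BoNT/A-DP and against the plan's own cautious defaults.

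The direction is certain from the text; the frequency is not known from the documents. The size is 0.57 points on the placebo rate per newly affected subject, assuming the planned 175, with a matching loss from the open-label BoNT/A-DP count. The 175 are the subjects at risk if all are re-treated, not the number affected. No claim is made that the between-arm contrast is materially distorted. This is a modest fault that is cheap to remove.

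**What to change.** In SAP 8.7.2 add, for placebo-first subjects only: if the known parts of the onset date allow onset on or after the first BoNT/A-DP injection, and the end date is not before that injection (or is missing, as in the existing first-dose rule), assign the event to the open-label phase and to BoNT/A-DP.

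Keep the cycle 1 default for BoNT/A-DP-first subjects. A rule sending every ambiguous event to the latest possible treatment would take true cycle 1 events out of the active arm in the placebo-controlled period.

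State in SAP 7.2.2.1 that day-1 and 1 January imputation does not override this assignment. Report the number of events it affects. Since protocol 12.4.2 carries the present rule, list the change in SAP section 9.

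The cost is a few lines of SAP text and a small change to the date program, with no new data. The downside is that some true placebo events will be counted under BoNT/A-DP, which is the cautious direction for the active drug.
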